### 5.3. Additional Eligibility Criteria

To assess any potential impact on participant eligibility with regard to safety, the investigator must refer to the IB and supplements, approved product labels, and/or local prescribing information for detailed information regarding warnings, precautions, contraindications, AEs, drug interactions, and other significant data pertaining to the study drugs.

Notwithstanding these minimum inclusion and exclusion criteria, investigators must also follow country specific guidelines where they exist when making decisions about participants who are eligible for study participation.

Participation in other interventional studies or non-interventional studies that require any type of assessment outside the local standard of care practices is generally not permitted, however for eligible subjects in South Africa only, co-enrolment in the AIDS Clinical Trial Group ACTG interventional study (A5392) could be exceptionally permitted after review and approval by the Medical Monitor.

#### **5.4. Screening/Baseline/Run-in Failures**

Screen failures are defined as participants who consent to participate in the clinical trial but are never subsequently randomized. In order to ensure transparent reporting of screen failure participants, meet the Consolidated Standards of Reporting Trials (CONSORT) publishing requirements, and respond to queries from Regulatory authorities, a minimal set of screen failure information is required including Demography, Screen Failure details, Eligibility Criteria, and Serious Adverse Events.

A single repeat of a procedure / lab parameter is allowed to determine eligibility (unless otherwise specified).

Participants are allowed to re-screen for this study one time. This will require a new participant number.

#### **5.5. Withdrawal/Stopping Criteria**

Participants permanently discontinuing study treatments prior to the Week 100 visit are considered to be withdrawn from the study treatments.

Participants who enter the Extension Phase but permanently discontinue participation in the Extension Phase prior to the CAB LA + RPV LA marketed product is locally available are considered withdrawn from the study treatments but are not considered withdrawn from the study because they will enter the Long Term Follow-up Phase.

Participants who enter the Extension Phase but permanently discontinue participation in the Extension Phase when the CAB LA + RPV LA marketed product is locally available must enter the Long Term Follow-up Phase if they withdraw from the study due to safety-related reasons only.

The participant may withdraw consent and discontinue participation in this study at any time at his/her own request. The investigator may also, at his or her discretion, discontinue the participant from participating in this study at any time (e.g., safety, behavioral or administrative reasons). Participants may have a temporary interruption to their study treatment for management of toxicities. If a participant withdraws from the study, he/she may request destruction of any samples taken, and the investigator must document this in the site study records. Withdrawn participants will not be replaced.

All participants who discontinue prematurely from the study, irrespective of arm, will be asked for additional information to establish the reason for withdrawal.

Participants are not obligated to state the reason for withdrawal. However, the reasons for withdrawal, or failure to provide a reason, must be documented by the Investigator on the Completion/Withdrawal section of the electronic case report form (eCRF). Every effort should be made by the Investigator to follow-up participants who withdraw from the study.

An in-clinic withdrawal visit will also be used to assess participants with ongoing AEs, and serious adverse events (SAEs) related & not related to study drug and also any laboratory abnormalities that are considered to be AEs or potentially harmful to the participant. The withdrawal visit will be distinct from visits conducted during the LTFU Phase.

After completing withdrawal assessments, all participants who received one or more injections of CAB LA+ RPV LA will subsequently enter the LTFU Phase initiating with the Month 3 LTFU visit. When CAB LA + RPV LA marketed product is locally available, entering the LTFU phase is only required if the subject withdraws due to safety-related reasons.

**Withdrawal decision coincides with a planned clinic visit:**

- For any participant who withdraws prematurely from the Maintenance or Extension Phase during a planned in-clinic study visit, withdrawal assessments and procedures are to be performed (according to the Time and Events Table (Section 7.1) instead of the assessments for the active planned visit during which the withdrawal decision is made.

**Withdrawal decision occurs between planned clinic visits:**

- In the event that a decision to withdraw a participant occurs between clinic visits, participants will be instructed to return for an unscheduled withdrawal visit (within 4 weeks of the last Q4W LA injection or within 8 weeks of the last Q8W LA injection received) during which withdrawal assessments according to the Time and Events Table (Section 7.1) will be completed. For participants who received one or more injections of CAB LA+ RPV LA **withdrawal assessments must occur prior to initiation of the next ART regimen.**

If withdrawal coincides with the active planned Week 52, Week 100, or Week 156 (Q4W arm) visits, HIV-1 RNA will only be assessed if the last HIV-RNA measurement from Week 48, Week 96, or Week 152 was  $\geq 50$  copies per mL (i.e. retest for viral load blip). This will ensure that only the Week 48, Week 96, and Week 152 viral load assessments or required retest will be counted towards the primary and secondary efficacy endpoint windows.

The in-clinic visit will be recorded as an unscheduled withdrawal visit with the following exception. A withdrawal visit and assessments coinciding with the planned Week 100 visit will be recorded as the Week 100 visit such that the participant can be considered a completer, consistent with the definition of study completer in Section 5.6.

**Participants may be prematurely discontinued from the study treatment for any of the following reasons:**

- Adverse event / Serious adverse event
- Protocol deviation
- Intolerability of injections
- Participant lost to follow-up
- Participant or Investigator non-compliance;
- Termination of the study by the Sponsor
- At the request of the participant, Investigator, GSK or ViiV Healthcare;
- The participant requires concurrent prohibited medications during the course of the study. The participant may remain in the study if in the opinion of the Investigator and the medical monitor; such medication will not interfere with the conduct or interpretation of the study or compromise the safety of the participant.

**Participants must be discontinued from study treatment for any of the following reasons:**

- Participants who are not eligible to continue into the Maintenance Phase.
- Participants who are not eligible, or do not wish to continue on to the Extension Phase.
- Virologic withdrawal criteria as specified in Section 5.5.4 are met;
- Participant requires substitution of ART;
- Participant requires substitution or dose reduction of CAB LA or RPV LA (oral bridging supply and potential for a second loading dose may be permissible following discussion with the Medical Monitor).
- Liver toxicity where stopping criteria are met and no compelling alternate cause is identified (see Section 5.5.1);
- Renal toxicity are met and no compelling alternate cause is identified;
- QT interval (QTc) interval >550 msec from three or more tracings separated by at least 5 minutes and considered causally related to IP.
- Grade 4 clinical AE considered causally related to study drug;
- Participant has a Grade 3 or higher rash or Grade 2 rash with evidence of systemic involvement and no compelling alternative cause is identified
- Participant withdrew consent

Efficacy data for participants withdrawing from the study will be considered evaluable up to the point at which they are withdrawn using the same criteria for evaluability as for participants who complete the study.

Safety data for all participants who receive any amount of study drug, including participants who withdraw from the study, will be included in evaluations of safety.

All data from the Withdrawal visit will be recorded, as they comprise an essential evaluation that should be done prior to discharging any participant from the study.

The following actions must be taken in relation to a participant who fails to attend the clinic for a required study visit:

- a. The site must attempt to contact the participant and re-schedule the missed visit as soon as possible.
- b. The site must counsel the participant on the importance of maintaining the assigned visit schedule and ascertain whether or not the participant wishes to and/or should continue in the study.
- c. In cases where the participant is deemed 'lost to follow up', the investigator or designee must make every effort to regain contact with the participant (where possible, 3 telephone calls and if necessary a certified letter to the participant's last known mailing address or local equivalent methods). These contact attempts should be documented in the participant's medical record.
- d. Should the participant continue to be unreachable, only then will he/she be considered to have withdrawn from the study with a primary reason of "Lost to Follow-up".

A participant may withdraw from study treatment at any time at his/her own request, or may be withdrawn at any time at the discretion of the investigator for safety, behavioral or administrative reasons. If a participant withdraws from the study, he/she may request destruction of any samples taken, and the investigator must document this in the site study records. Please refer to Section 11.5 for additional guidance for sample destruction request.

### 5.5.1. Liver Chemistry Stopping Criteria

**Liver chemistry stopping and increased monitoring criteria** have been designed to assure participant safety and evaluate liver event etiology.

IP will be stopped if any of the following liver chemistry criteria are met:

- ALT  $\geq 3xULN$  and bilirubin  $\geq 2xULN$  (>35% direct bilirubin, bilirubin fractionation required).
- NOTE: serum bilirubin fractionation should be performed if testing is available. If testing is unavailable, sites should evaluate the presence of detectable urinary bilirubin on dipstick, indicating direct bilirubin elevations and suggesting liver injury. If testing is unavailable and a participant meets the criterion of total bilirubin  $\geq 2xULN$ , then the event meets liver stopping criteria.
- ALT  $\geq 8xULN$ .

- ALT  $\geq 3$ xULN (if Baseline ALT is  $< \text{ULN}$ ) with symptoms or worsening of acute hepatitis or hypersensitivity such as fatigue, nausea, vomiting, right upper quadrant pain or tenderness, fever, rash, or eosinophilia, OR;
- ALT  $\geq 3$ x Baseline ALT with symptoms or worsening of acute hepatitis or hypersensitivity such as fatigue, nausea, vomiting, right upper quadrant pain or tenderness, fever, rash, or eosinophilia;
- ALT  $\geq 5$ xULN and  $< 8$ xULN that persists  $\geq 2$  weeks (with bilirubin  $< 2$  ULN & no signs or symptoms of acute hepatitis or hypersensitivity).
- ALT  $\geq 5$ xULN but  $< 8$ xULN and cannot be monitored weekly for  $> 2$  weeks.

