18. Evidence of Hepatitis B virus (HBV) infection based on the results of testing at Screening for Hepatitis B surface antigen (HBsAg), Hepatitis B core antibody (anti-HBc), Hepatitis B surface antibody (anti-HBs) and HBV DNA as follows:
- a. •Participants positive for HBsAg are excluded;
  - b. •Participants negative for anti-HBs but positive for anti-HBc (negative HBsAg status) and positive for HBV DNA are excluded
- Note:* Participants positive for anti-HBc (negative HBsAg status) and positive for anti-HBs (past and/or current evidence) are immune to HBV and are not excluded.
19. Asymptomatic individuals with chronic hepatitis C virus (HCV) infection will not be excluded, however Investigators must carefully assess if therapy specific for HCV infection is required; participants who are anticipated to require HCV treatment within 12 months must be excluded. (HCV treatment on study may be permitted post Week 52, following consultation with the medical monitor)
20. Participants with HCV co-infection will be allowed entry into this study if:
- a. Liver enzymes meet entry criteria
  - b. HCV Disease has undergone appropriate work-up, and is not advanced, and will not require treatment prior to the Week 52 visit. Additional information (where available) on participants with HCV co-infection at screening should include results from any liver biopsy, Fibroscan, ultrasound, or other fibrosis evaluation, history of cirrhosis or other decompensated liver disease, prior treatment, and timing/plan for HCV treatment.
  - c. In the event that recent biopsy or imaging data is not available or inconclusive, the Fib-4 score will be used to verify eligibility
    - i. Fib-4 score >3.25 is exclusionary
    - ii. Fib-4 scores 1.45 – 3.25 requires Medical Monitor consultation

Fibrosis 4 Score Formula:

$$(Age \times AST) / (Platelets \times (\sqrt{ALT}))$$
21. Unstable liver disease (as defined by any of the following: presence of ascites, encephalopathy, coagulopathy, hypoalbuminemia, esophageal or gastric varices, or persistent jaundice or cirrhosis), known biliary abnormalities (with the exception of Gilbert's syndrome or asymptomatic gallstones or otherwise stable chronic liver disease per investigator assessment)
22. History of liver cirrhosis with or without hepatitis viral co-infection.
23. Ongoing or clinically relevant pancreatitis

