31. Any acute laboratory abnormality at Screening, which, in the opinion of the investigator, would preclude the participant's participation in the study of an investigational compound
32. Participant has estimated creatine clearance  $< 50$  mL/min per  $1.73\text{m}^2$  via Chronic Kidney Disease-Epidemiology Collaboration (CKD-EPI) Method
33. Alanine aminotransferase (ALT)  $\geq 3 \times$  ULN

Concomitant Medications

34. Exposure to an experimental drug (with the exception of those in the ATLAS study including CAB, CAB LA, and RPV LA) or experimental vaccine within either 30 days, 5 half-lives of the test agent, or twice the duration of the biological effect of the test agent, whichever is longer, prior to Day 1 of this study;
 
35. Treatment with any of the following agents within 28 days of Screening:
 
 
• radiation therapy;
 
• cytotoxic chemotherapeutic agents;
 
• tuberculosis therapy with the exception of isoniazid (isonicotinylhydrazid, INH);
 
• anti-coagulation agents;
 
• Immunomodulators that alter immune responses such as chronic systemic corticosteroids, interleukins, or interferons. Note: Participants using short-term (e.g. <math>\leq 21</math> days) systemic corticosteroid treatment; topical, inhaled and intranasal corticosteroids are eligible for enrolment.
 
 
36. Treatment with an HIV-1 immunotherapeutic vaccine within 90 days of Screening
 
37. Treatment with any agent, except recognized ART as allowed above, with documented activity against HIV-1 within 28 days of study Day 1. Treatment with acyclovir/valacyclovir is permitted.
 
38. Use of medications which are associated with Torsade de Pointes. (See SPM for a list of relevant medications)
 
39. Current or prior history of etravirine (ETR) use
 
40. Current use of tipranavir/ritonavir or fosamprenavir/ritonavir
 
41. Participants receiving any prohibited medication and who are unwilling or unable to switch to an alternate medication. Note: Any prohibited medications that decrease CAB or RPV concentrations should be discontinued for a minimum of four weeks or a minimum of three half-lives (whichever is longer) prior to the first dose and any other prohibited medications should be discontinued for a minimum of two weeks or a minimum of three half-lives (whichever is longer) prior to the first dose

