#### **When any of the liver chemistry stopping criteria is met, do the following:**

- Immediately hold IP. If on LA therapy, **do not** administer another injection until approval is received from the ViiV Safety and Labelling Committee.
- Report the event to the Medical Monitor within 24 hours of learning its occurrence.
- Complete the liver event eCRF and SAE eCRF, where applicable.
- Complete the liver imaging and/or liver biopsy eCRFs if these tests are performed.
- Perform liver event follow up assessments (described below), and monitor the participant until liver chemistries resolve, stabilize, or return to Baseline values as described below.
- Make every reasonable attempt to have participants return to clinic within 24 hours for repeat liver chemistries, liver event follow-up assessments (see below), and close monitoring.
- A specialist or hepatology consultation is recommended.
- Monitor participants twice weekly until liver chemistries (ALT, AST, alkaline phosphatase, bilirubin) resolve, stabilize or return to within Baseline values.

Make every attempt to carry out the **liver event follow-up assessments** described below:

- Viral hepatitis serology including:
  - Hepatitis A immunoglobulin M (IgM) antibody;
  - Hepatitis B surface antigen (HBsAg) and Hepatitis B Core Antibody (IgM);
  - Hepatitis C RNA;
  - Hepatitis E IgM antibody;
  - Cytomegalovirus IgM antibody;

- Epstein-Barr viral capsid antigen IgM antibody (or if unavailable, obtain heterophile antibody or monospot testing);
- Syphilis screening;
- Drugs of abuse screen including alcohol;
- Serum acetaminophen test (N-acetyl-para-aminophenol [APAP] adduct test). The site must contact GSK when this test is required. Please refer to the central laboratory manual.
- Blood sample for pharmacokinetic (PK) analysis, obtained during follow up assessments. Record the date/time of the PK blood sample draw and the date/time of the last dose of investigational product prior to blood sample draw on the eCRF. If the date or time of the last dose is unclear, provide the participant's best approximation. If the date/time of the last dose cannot be approximated OR a PK sample cannot be collected in the time period indicated above, do not obtain a PK sample. Instructions for sample handling and shipping are in the SPM.
- Serum creatine phosphokinase (CPK) and lactate dehydrogenase (LDH);
- Fractionated bilirubin, if total bilirubin is greater than 1.5xULN;

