#### **5.5.1.4.2. Drug Restart Following Transient Resolving Liver Events Not Related to IP**

Approval by the VSLC for drug restart or additional IM administration can be considered where:

- Abnormalities in liver chemistries have a clear underlying cause (e.g., biliary obstruction, hypotension, acute viral hepatitis) and liver chemistries have significantly improved.
- If definitive non-study drug related diagnosis, restart will be considered once ALT < 3x ULN (for participants with baseline ALT < 1.5x ULN) or < 3x baseline ALT value (for participants with baseline ALT > 1.5x ULN).
- Ethics Committee or Institutional Review Board approval of drug restart must be obtained, as required.
- If restart / redosing of drug is approved by the VSLC in writing, the participant must be provided with a clear description of the possible benefits and risks of drug administration, including the possibility of recurrent, more severe liver injury or death.
- The participant must also provide signed informed consent specifically for the restart. Documentation of informed consent must be recorded in the study chart.

Study drug must be administered at the dose specified by the VSLC. Participants approved by the VSLC for restarting or re-dosing IP must return to the clinic once a week for liver chemistry tests for a minimum of one month and thereafter for as long as clinically indicated and then laboratory monitoring may resume as per protocol. If protocol defined stopping criteria for liver chemistry elevations are met, study drug must be stopped.

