**Table 8 Safety Laboratory Assessments**

Hematology			
Platelet count	Automated WBC differential:		
RBC count	Neutrophils		
WBC count (absolute)	Lymphocytes		
Hemoglobin	Monocytes		
Hematocrit	Eosinophils		
MCV	Basophils		
Clinical Chemistry			
BUN	Potassium	AST	Total bilirubin a
Creatinine	Chloride	ALT	Albumin
Glucose c	Total CO 2	Alkaline phosphatase	Creatine phosphokinase
Sodium	Lipase	Phosphate	Creatinine clearance b
Fasting Lipid Paneld			
Total cholesterol			
HDL cholesterol			
LDL cholesterol			
Triglycerides			
Other Tests			
Plasma HIV-1 RNA e			
CD4+ and CD8+ cell counts [CD4/CD8 ratio] f			
Peripheral Blood Mononuclear Cells (PBMCs): Day 1, Week 48, Week 96, Week 152 Withdrawal only			
Hepatitis B (HBsAg), anti-HBc, anti-HBsAg, and hepatitis C antibody (Screening) g			
Syphilis serology + Reflex Rapid Plasma Reagin (RPR) (Screening and Baseline)			
Prothrombin Time (PT)/International Normalized Ratio (INR)/ Partial Thromboplastin Time (PTT)			
Pregnancy test for women of childbearing potential h			
Urinalysis, urine albumin/creatinine ratio, and urine protein/creatinine ratio, urine phosphate			
Genetics Sample			
Follicle stimulating hormone (FSH) and estradiol (only for instances when postmenopausal status is questionable)			

MCV = mean corpuscular volume, RBC = red blood cells, WBC = white blood cells, BUN = Blood urea nitrogen, AST=aspartate aminotransferase, ALT = alanine aminotransferase, CO2 = carbon dioxide, HDL = high density lipoprotein, LDL = low density lipoprotein, HBsAg= hepatitis B virus surface antigen, PT/INR = prothrombin time/international normalized ratio.

- Direct bilirubin will be reflexively performed for all total bilirubin values  $>1.5 \times \text{ULN}$ .
- Glomerular filtration rate (GFR) will be estimated by the central laboratory using the Chronic Kidney Disease Epidemiology Collaboration (CKD-EPI) [Levey, 2009].
- For fasting glucose assessments, an overnight fast is preferred; however, a minimum of a 6-hour fast is acceptable for participants with afternoon appointments.
- For fasting lipids assessments, an overnight fast is preferred; however, a minimum of a 6-hour fast is acceptable for participants with afternoon appointments.
- For participants meeting virologic withdrawal criteria, plasma samples will be analyzed in attempt to obtain genotype/phenotype data.

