**Table 9 Reporting of Serious Adverse Events and Other Events**

Type of Event a	Initial Reports		Follow-up Information on a Previous Report	
	Time Frame	Documents	Time Frame	Documents
All SAEs	24 hours	"SAE" data collection tool	24 hours	Updated "SAE" data collection tool
Cardiovascular or death event	Initial and follow-up reports to be completed when the cardiovascular event or death is reported a	"CV events" and/or "death" data collection tool(s) if applicable	Initial and follow-up reports to be completed when the cardiovascular event or death is reported a	Updated "CV events" and/or "death" data collection tool(s) if applicable
Pregnancy	24 hours	"Pregnancy Notification Form"	Within 24 hours of investigator awareness of pregnancy outcome	"Pregnancy Follow-up Form" and SAE if required
Seizure or suspected seizure	24 hours	eCRF	24 hours	eCRF
Suspected ABC HSR in participants receiving Oral SOC during the Long-Term Follow-Up Phase b	1 week	ABC HSR eCRF	1 week	Updated ABC HSR eCRF
ALT $\geq$ 3 $\times$ ULN and bilirubin $\geq$ 2 $\times$ ULN (>35% direct) (or ALT $\geq$ 3 $\times$ ULN)	24 hours c	"SAE" data collection tool. "Liver Event eCRF" and "Liver Imaging" and/or "Liver Biopsy" eCRFs, if applicable d	24 hours	Updated "SAE" data collection tool/"Liver Event" documents d

Type of Event e	Initial Reports		Follow-up Information on a Previous Report	
	Time Frame	Documents	Time Frame	Documents
ALT ≥ 5 × ULN that persists ≥ 2 weeks	24 hours c	Liver Event eCRF d	24 hours	Updated Liver Event eCRF d
ALT ≥ 8 × ULN	24 hours c	Liver Event eCRF d	24 hours	Updated Liver Event eCRF d
ALT ≥ 3 × ULN (if baseline ALT is < ULN) or ALT ≥ 3 fold increase from baseline value with appearance or worsening of symptoms of hepatitis or hypersensitivity	24 hours c	Liver Event eCRF d	24 hours	Updated Liver Event eCRF d

- Additional details and time frames for reporting supplementary information for cardiovascular and death events are provided in Section 7.4.3.7 and Section 7.4.3.8, respectively.
- ABC HSR eCRF only required if event meets one of the ICH E2A definitions of seriousness.
- GSK must be contacted at onset of liver chemistry elevations to discuss participant safety.

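### The persistent-ALT stopping criterion drops out when symptoms or bilirubin ≥2×ULN are present, and the other criteria in Section 5.5.1 do not catch all the participants it releases

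*Protocol*

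**What the plan says.** Section 5.5.1 lists six criteria, any one of which stops investigational product (IP). Paraphrased:

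1. ALT ≥3×ULN with bilirubin ≥2×ULN and more than 35% direct. The direct fraction is waived only where it cannot be tested.
2. ALT ≥8×ULN.
3. ALT ≥3×ULN with symptoms, if Baseline ALT is below ULN.
4. ALT at least three times "Baseline ALT with symptoms or worsening of acute hepatitis or hypersensitivity such as fatigue, nausea, vomiting" and so on.
5. ALT ≥5 and <8×ULN for at least two weeks, restricted in parentheses to bilirubin below 2 "ULN & no signs or symptoms of acute hepatitis or hypersensitivity".
6. ALT ≥5 and <8×ULN where weekly monitoring is not possible. There is no bilirubin or symptom condition.

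Table 9 (Section 7.4.3.4) lists the event in criterion 5 for reporting as "ALT ≥ 5 × ULN that persists ≥ 2 weeks", with neither condition.

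Other provisions decide who can reach these criteria:

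- Exclusion 33 (Section 5.2) removes only ALT ≥3×ULN at Screening.
- Exclusion 21 bars known biliary abnormalities "with the exception of Gilbert's syndrome or asymptomatic gallstones", among other exceptions.
- The restart rule in Section 5.5.1.4.2 has a threshold of "3x baseline ALT value (for participants with baseline ALT > 1.5x ULN"), so the protocol expects raised Baselines.
- A footnote to Table 8 states: "Direct bilirubin will be reflexively performed for all total bilirubin values" above 1.5×ULN.

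Once a criterion is met, Section 5.5.1.1 requires an immediate hold. Sites must not "administer another injection until approval is received from the ViiV Safety and Labelling Committee". Twice-weekly monitoring and a liver work-up follow.

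**The concern.** The restriction in criterion 5 is harmless only if criteria 1 to 4 catch everyone it removes. They do not, so in part of the range the rule runs backwards: adding hepatitis symptoms, or raising bilirubin past 2×ULN, takes away a mandatory stop that the milder picture would have triggered. The protocol gives no reason for this.

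What is at stake is the automatic hold, committee approval before the next long-acting injection, twice-weekly tests and the work-up. The liver safety panel (Section 5.5.1.2) and committee adjudication (Section 7.4.5.1) are also reserved for participants who meet a stopping criterion. For asymptomatic Grade 3 laboratory abnormalities, Section 7.4.4.3 lets IP continue after discussion with the Medical Monitor if there is compelling evidence of another cause, but makes an exception for the liver stopping criteria. A participant outside those criteria is outside the exception. (The ALT grade cut-offs are in Appendix 2, which was not available here. That ALT of 5 to <8×ULN is Grade 3 is an assumption.)

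**Working it through.** There is no stated figure to reproduce; the check is of the rule's logic. ALT and Baseline ALT (B) are in ×ULN. ALT is between 5 and <8 for at least two weeks and weekly monitoring is possible, so criterion 6 is not triggered. Exclusion 33 gives B <3.

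**Group (a): symptoms present, bilirubin <2×ULN.**

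- Criterion 1 fails on bilirubin, criterion 2 because ALT <8, and criterion 5 because of the symptoms.
- Criterion 3 applies only if B <1.
- Criterion 4 applies only if ALT ≥3B.

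The participant is therefore missed when 5 ≤ ALT < min(8, 3B). This range is non-empty once 3B >5, that is B >5/3 = 1.67. It fills the band once 3B ≥8, that is B ≥8/3 = 2.67.

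| Baseline (×ULN) | 3B | ALT range missed |
|---|---|---|
| up to 1.66 | below 5 | none |
| 2.0 | 6.0 | 5 to <6 |
| 2.25 | 6.75 | 5 to <6.75 |
| 2.5 | 7.5 | 5 to <7.5 |
| 2.67 to <3 | 8 or more | 5 to <8 (all) |

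Example: at B = 2.5 and ALT = 7, 3B = 7.5 exceeds 7, so criterion 4 is not met. With symptoms no criterion applies; without symptoms criterion 5 stops IP.

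**Group (b): bilirubin ≥2×ULN, at most 35% direct.**

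- Criterion 1 fails on the direct fraction. Because direct bilirubin is measured by reflex above 1.5×ULN, the waiver for unavailable testing will seldom apply.
- Criterion 5 fails on bilirubin.
- Without symptoms, criteria 3 and 4 cannot apply, so the whole 5 to <8 band is missed at every Baseline.
- With symptoms, criterion 3 or 4 applies except in the ranges tabulated for group (a).

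Example: at ALT 7×ULN, 30% direct and no symptoms, bilirubin of 1.9×ULN stops IP and 2.1×ULN does not.

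**Enumeration.** The grid was ALT 5.00 to 7.95 by 0.05 (60 values), Baseline 0.30 to 2.99 by 0.01 (270 values), symptoms yes or no, and four bilirubin/direct pairs (1.0/20%, 1.9/30%, 2.5/30%, 2.5/50%). That is 60 × 270 × 2 × 4 = 129,600 combinations.

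| Block | Uncovered |
|---|---|
| Symptoms; 1.0/20%, 1.9/30% and 2.5/30% | 3 × 5,010 = 15,030 |
| No symptoms; 2.5/30% | 60 × 270 = 16,200 |
| All other blocks | 0 |
| Total as written | 31,230 |
| Total with the parenthesis deleted | 0 |

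These are logical combinations, not expected participants. For ALT of 1 to <5 or 8 to <12×ULN, the deletion changes no decision.

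**The case against.** The literal logic is hard to dispute. The case on the other side is about unseen text, other safeguards and rarity.

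- **Appendix 3.** Its title covers required actions as well as restart, and Section 5.5.1.4.1 cites Section 11.3 when it mentions the stopping criteria. It was not in the part of the protocol available here. However, its listed sub-sections concern restart only, and Sections 5.5 and 5.5.1.4 name Section 5.5.1 as the source of the criteria. Different text in Appendix 3 would contradict Section 5.5.1, not repair it.
- **Other safeguards.** Table 9 requires a report within 24 hours for every participant in both groups, and its footnote requires contact with the sponsor at onset. Section 7.4.4.2 requires Medical Monitor consultation at ALT ≥3×ULN, and Section 5.5.1.1 weekly follow-up at ≥5×ULN. None of these depends on a judgement of cause, but none is a hold. Withdrawal for suspected drug-induced liver injury, no further injections after suspected hypersensitivity (both Section 2.3.1) and withholding for related Grade 3 events (Section 7.4.4.3) do stop dosing, but only on a judgement of cause. None brings committee review. The Section 7.4.4.3 clause on asymptomatic abnormalities bears on group (b) without symptoms, not on group (a).
- **Small practical difference.** With dosing every 4 or 8 weeks, a hold mostly affects the next injection.
- **Rarity.** Section 2.3.1 reports transaminitis in under 1% of participants in the cabotegravir programme. If that rate applied here, it would mean fewer than about 10 of 1020 (0.01 × 1020 = 10.2) with any transaminitis, and the gaps need further coincidences.
- **Gilbert's syndrome.** The direct-fraction condition sensibly keeps these participants out of criterion 1. It is no reason to remove the ALT-only stop that others have.

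The safeguards and the rarity stand, and they limit the weight of the point. They do not close the gap.

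**Conclusion.** The concern holds. As written, Section 5.5.1 leaves two groups without a mandatory stop at persistent ALT of 5 to <8×ULN, although a milder presentation at the same ALT is stopped. Group (a) is confined to Baseline ALT above 1.67 and below 3×ULN, and to ALT below three times Baseline. Group (b) without symptoms is missed at every Baseline. Criterion 6 and Table 9 cover the same ALT territory with neither condition, which suggests the exclusion was not intended.

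The conclusion assumes that weekly monitoring is possible, that Baseline ALT stays within the Screening limit, that the bilirubin bound in criterion 5 means 2×ULN, and that Appendix 3 does not state different criteria. Few participants would be affected. It is a participant-safety point that should be corrected, and it has no bearing on the efficacy analysis.

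**What to change.** Delete the parenthesis from the fifth criterion in Section 5.5.1, so that it covers ALT ≥5×ULN and <8×ULN persisting for two weeks or more, whatever the bilirubin or symptoms. This agrees with the Table 9 row, since ALT ≥8×ULN has its own criterion. Table 9 needs no change, and Appendix 3 should be checked for any restatement.

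No new sample or procedure is needed. The cost is that a few participants with benign indirect hyperbilirubinaemia or a raised Baseline ALT would be held pending committee review. Restart then needs written committee approval, separate consent and, where required, ethics approval. An interruption also carries the resistance risk described in Section 6.9.1. For a definitive diagnosis unrelated to study drug, Section 5.5.1.4.2 lets restart be considered once ALT is below three times Baseline where Baseline exceeds 1.5×ULN (for example below 3 × 2.5 = 7.5×ULN). That limits the hold in group (a). Group (b) participants with Baseline below 1.5×ULN would have to fall below 3×ULN first.
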